7.3.2. Treatment Assignment, and Randomization

Block randomization with stratification for severity of ARDS (mild/moderate [PaO₂/FiO₂ > 100 to \leq 300 mmHg] vs severe [PaO₂/FiO₂ \leq 100 mmHg]) and investigational site will be used. Participants will be randomly assigned to either ruxolitinib 5 mg BID, ruxolitinib 15 mg BID, or placebo. All participants will be centrally assigned to study treatment using an IRT system. The randomization schedule will be generated by a sponsor-independent statistician and sent directly to the IRT vendor without being provided to the Sponsor. Before the study is initiated, the URL and contact information (if applicable) for the IRT and/or the log-in information and directions for the IRT will be provided to each site. Full details will be provided in the IRT manual.

7.4. Treatment Blinding

Participants, investigator staff, persons performing the assessments, and the Incyte study team will remain blind to the identity of the treatment from the time of randomization until database lock using the following methods: (a) randomization data will be kept strictly confidential until the time of unblinding and will not be accessible by anyone else involved in the study, and (b) the identity of the treatments will be concealed by the use of study treatments that are all identical in packaging, schedule of administration, appearance, taste, and odor.

Unblinding will occur in the case of participant emergencies and at the conclusion of the study. If the investigator feels that unblinding prior to completion of the treatment period is clinically indicated, consult the Medical Monitor.

7.5. Dose Modification

7.5.1. Dose Modifications

Dose reductions or interruptions for worsening cytopenias or nonhematologic toxicity attributed to ruxolitinib are permitted to allow the participant to continue on study treatment (see Section 7.6.2 for additional guidance). For the purpose of dose modifications, Table 6 will be used to guide dose reductions based on treatment arm assignment.

Table 6:Ruxolitinib Dose Levels

Treatment Arm	Dose Level 1 (Initial Dose)	Dose Level -1
Ruxolitinib/placebo: 5 mg BID	5 mg BID	5 mg QD
Ruxolitinib/placebo: 15 mg BID	15 mg BID	5 mg BID

Dose modifications must be reported in the appropriate eCRFs.

7.5.1.1. Follow-Up on Potential Drug-Induced Liver Injury Cases

Transaminase increase combined with total bilirubin increase may be indicative of potentially severe DILI, which should be considered a clinically important event and assessed appropriately to establish the diagnosis. The required clinical information, as detailed in the following text, should be sought to obtain the medical diagnosis of the most likely cause of the observed laboratory abnormalities.

The threshold for potential DILI may depend on the participant's baseline AST/ALT and total bilirubin; participants meeting any of the following criteria will require further follow-up as outlined as follows:

- For participants with normal ALT and AST and total bilirubin at baseline: AST or $ALT > 3.0 \times ULN$ combined with total bilirubin $> 2.0 \times ULN$.
- For participants with elevated AST or ALT or total bilirubin value at baseline: (AST or ALT > 2 × baseline) OR (AST or ALT > 300 U/L), whichever occurs first, combined with (total bilirubin > 2 × baseline AND > 2.0 × ULN).

Because DILI is essentially a diagnosis of exclusion, other causes of abnormal liver tests should be considered and their role clarified before DILI is assumed as the cause of liver injury.

A detailed history, including relevant information such as review of ethanol consumption, concomitant medications, herbal remedies, supplement consumption, and history of any pre-existing liver conditions or risk factors, should be collected.

Laboratory tests should include ALT, AST, total bilirubin, direct and indirect bilirubin, gamma-glutamyl transferase, glutamate dehydrogenase, prothrombin time/international normalized ratio, ALP, albumin, and CK.

7.6. Additional Treatment Guidance

7.6.1. Treatment Compliance

Treatment will be recorded on the appropriate eCRF.

7.6.2. Recommended Treatment of Adverse Events

Dose reductions or interruptions for worsening cytopenias attributed to ruxolitinib/placebo are permitted to allow the participant to continue on study treatment. Table 6 describes dose levels of ruxolitinib by treatment arm. Dose adjustments for different ranges of cytopenias are described in the following text. Use of transfusion support is allowed during the study.

7.6.2.1. Neutropenia

Grade 3 (ANC < 1.0 to 0.5×10^9 /L): Reduce by 1 dose level, monitor ANC daily until resolved to \leq Grade 2, and then resume initial dose level.

Grade 4 (ANC < 0.5×10^9 /L): Hold dose, monitor ANC daily until resolved to \leq Grade 3, and then resume at 1 dose level lower. If resolves to \leq Grade 2, can resume at initial dose level.

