bronchitis, and the possibility of developing anemia, bleeding, fatigue, and/or shortness of breath. In healthy volunteers, rheumatoid arthritis patients, and patients with pancreatic cancer or hormone-refractory prostate cancer, the effects on hematopoietic proliferation are less pronounced, presumably because of greater bone marrow reserve. The most frequent nonhematologic AEs were mild, reversible increases in ALT and AST; bruising; hypercholesterolemia; dizziness; headache; and urinary tract infections. Tuberculosis has been infrequently reported in patients receiving ruxolitinib to treat MF (< 1/100 patients). The symptoms of tuberculosis include chronic cough with blood-tinged sputum, fever, night sweats, and weight loss. There may be risks associated with rapid discontinuation of ruxolitinib.

Patients with MF, particularly those who have stopped taking ruxolitinib suddenly after long-term administration, have reported return of MF symptoms such as fatigue, bone pain, fever, pruritus, night sweats, symptomatic splenomegaly, and weight loss. In very few MF patients, respiratory distress, disseminated intravascular coagulation, and multiorgan failure have been reported.

Hepatitis B viral load increases, with and without associated elevations in ALT and AST, have been reported in patients with chronic hepatitis B infections taking ruxolitinib. The effect of ruxolitinib on viral replication in patients with chronic hepatitis B virus is unknown. A rare disease called PML has been reported during treatment with ruxolitinib. It is important to note that PML and infections are complications associated with MF that have been previously described in the absence of ruxolitinib. Additionally, non-melanoma skin cancers, including basal cell, squamous cell, and a rare and aggressive type of skin cancer called Merkel cell carcinoma have been reported in patients who took ruxolitinib; it is unknown whether this was due to ruxolitinib treatment.

In the presence of potent CYP3A4 inhibitors (see Appendix D), there is the possibility of increased exposure to ruxolitinib. A dose adjustment for the 15 mg BID ruxolitinib/placebo group is required when coadministered with potent CYP3A4 inhibitors (see Section 7.2.1.2). No dose adjustment of ruxolitinib is required for participants assigned to 5 mg BID ruxolitinib/placebo.

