7.2.1.2. Coadministration With Potent CYP3A4 Inhibitors

Coadministration of ruxolitinib and potent CYP3A4 inhibitors may result in increased ruxolitinib exposure; in the setting of potent CYP3A4 inhibitors (see Appendix D for a list), participants assigned **to the 15 mg BID ruxolitinib/placebo arm only** should be reduced 1 dose level (see Table 6) with daily complete blood cell count monitoring during the period of coadministration.

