7.2.1.3. CRRT and Intermittent Hemodialysis

If a participant requires CRRT during the study treatment period, the ruxolitinib/placebo dose frequency should be reduced from BID to QD. If a participant requires intermittent hemodialysis during the study treatment period, the assigned ruxolitinib/placebo dose should only be given on hemodialysis days and following each hemodialysis session.

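### Table 6 gives each arm one reduction level, shared by the CYP3A4 rule (15 mg arm) and the toxicity rules; the separate CRRT rule is not aligned with it, and no precedence is stated

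*Protocol*

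**What the plan says.** Section 7.5.1 states that "Table 6 will be used to guide dose reductions based on treatment arm assignment". Table 6 has two columns: Dose Level 1, labelled as the initial dose, and Dose Level -1. The row for the higher arm (arm, initial dose, reduced dose) reads "Ruxolitinib/placebo: 15 mg BID 15 mg BID 5 mg BID". In the lower arm, 5 mg BID goes to 5 mg QD. There is no further level in either arm.

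These rules then change the dose:

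- **Potent CYP3A4 inhibitors (Section 7.2.1.2).** Participants in the 15 mg arm, and only they, "should be reduced 1 dose level (see Table 6) with daily complete blood cell count monitoring during the period of coadministration". Section 5.6 calls this adjustment required, and adds: "No dose adjustment of ruxolitinib is required for participants assigned to 5 mg BID ruxolitinib/placebo".
- **CRRT (Section 7.2.1.3).** In either arm, "the ruxolitinib/placebo dose frequency should be reduced from BID to QD". Table 6 is not cited.
- **Grade 3 neutropenia (Section 7.6.2.1).** "Reduce by 1 dose level, monitor ANC daily until resolved to" Grade 2 or better, "and then resume initial dose level".
- **Grade 4 neutropenia (7.6.2.1) and platelets below 20 × 10⁹/L (7.6.2.2).** Hold, then restart one level lower; a later return to the initial level is optional.
- **Grade 3 nonhematologic toxicity (7.6.2.3).** One level down until resolved; the level to return to is not named.

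No section ranks these rules, says what a one-level reduction means for someone already at Level -1, or limits the return to the initial level while an inhibitor or CRRT continues.

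**The concern.** A one-step table works if only one reason for reduction applies at a time. Here, overlapping reasons are foreseeable. Section 7.2.1.1 permits azole prophylaxis, and Appendix D lists posaconazole, voriconazole and lopinavir/ritonavir as strong inhibitors. Section 2.1 names acute kidney injury as a complication of severe disease, and Section 7.2.1.3 provides for dialysis on study. Section 5.6 describes dose-dependent neutropenia with this drug, although in myelofibrosis with longer and generally higher dosing.

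Two things are at stake. The first is safety: one section, followed as written, can send a participant just recovered from neutropenia to a dose that another section does not allow at that moment. The overdose definition (Section 11.9, more than 30 mg in 24 hours) would not flag it, because the return dose is exactly 30 mg. The second is the meaning of the dose arms: two sites could follow different sections and both be within the protocol. The compliance measure in SAP Section 6.5 uses the prescribed dose after modifications, so it would not show this. The daily-dose summary in SAP Section 6.4 would show the spread but not its cause.

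**Working it through.** The plan gives no figure to reproduce. The check applies the rules as written and computes mg/day = dose per administration × administrations per day.

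**Inputs (Table 6, Sections 7.2.1.2 and 7.2.1.3)**

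- 5 mg arm: Level 1 = 5 × 2 = 10 mg/day; Level -1 = 5 × 1 = 5 mg/day (a 50% cut).
- 15 mg arm: Level 1 = 15 × 2 = 30 mg/day; Level -1 = 5 × 2 = 10 mg/day (a 67% cut).
- Inhibitor: 15 mg arm moves to Level -1; 5 mg arm unchanged.
- CRRT: BID becomes QD. Where both apply, I assume both adjustments are made.

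| Arm | Inhibitor | CRRT | Before toxicity (mg/day) | Level -1 as tabulated (mg/day) | Literal return to Level 1 (mg/day) |
|---|---|---|---|---|---|
| 5 mg | no | no | 5 mg BID (10) | 5 mg QD (5) | 5 mg BID (10) |
| 5 mg | yes | no | 5 mg BID (10) | 5 mg QD (5) | 5 mg BID (10) |
| 5 mg | no | yes | 5 mg QD (5) | 5 mg QD (5) | 5 mg BID (10) |
| 5 mg | yes | yes | 5 mg QD (5) | 5 mg QD (5) | 5 mg BID (10) |
| 15 mg | no | no | 15 mg BID (30) | 5 mg BID (10) | 15 mg BID (30) |
| 15 mg | yes | no | 5 mg BID (10) | 5 mg BID (10) | 15 mg BID (30) |
| 15 mg | no | yes | 15 mg QD (15) | 5 mg BID (10) | 15 mg BID (30) |
| 15 mg | yes | yes | 5 mg QD (5) | 5 mg BID (10) | 15 mg BID (30) |

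**Reading the table**

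1. *15 mg arm, inhibitor.* The participant is already at Level -1, so a one-level reduction has nowhere to go. The literal return is 30/10 = 3 times the pre-toxicity dose and contradicts Sections 7.2.1.2 and 5.6 while coadministration continues.
2. *5 mg arm, CRRT (with or without an inhibitor).* The reduction is 5 to 5 mg/day, or 0%. The literal return is 10/5 = 2 times and contradicts Section 7.2.1.3.
3. *15 mg arm, CRRT.* The tabulated step lowers the daily dose (15 to 10 mg) but is BID, against the QD of Section 7.2.1.3. Level -1 with QD kept would be 5 mg/day, so two readings exist. The literal return is 30/15 = 2 times.
4. *15 mg arm, inhibitor and CRRT.* Moving to the tabulated Level -1 is 10/5 = 2 times the current daily dose, under an instruction to reduce. The literal return is 30/5 = 6 times.

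Three combinations give no conflict: either arm with neither trigger, and the 5 mg arm with an inhibitor alone. The other five do. Intermittent hemodialysis is left out, because daily totals would need a session schedule that the protocol does not give.

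**The case against.** The best reply is that the rules can be read cumulatively. Section 7.2.1.2 holds for as long as the inhibitor is given, and recovery of the neutrophil count does not end that period. On that reading the return is to whatever dose the inhibitor allows, and the threefold gap disappears. If no lower level existed, no toxicity reduction was made, so there is nothing to resume. The protocol also leaves discretion: Section 7.2.1.1 lets the investigator reduce or hold for suspected drug toxicity, Section 7.2.1 offers the medical monitor when a concomitant drug raises doubt, and Section 7.6.2 permits interruptions as well as reductions.

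Part of this stands. Holding is available, so an empty or zero step does not leave a site without an option. The cumulative reading is reasonable, but no section states it, and Table 6 fixes the initial dose by assigned arm. The nothing-to-resume argument fails when the order is reversed: a 15 mg arm participant reduced to 5 mg BID for Grade 3 neutropenia who then starts an inhibitor does have a dose to resume when the count recovers. The discretion covers reducing and holding; it does not say how the Grade 3 return applies while an inhibitor or CRRT continues.

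A reader might go further and infer that all three sets of rules draw on Table 6, that every toxicity rule forces a return to full dose, or that every overlap raises the dose. The documents do not support that. The CRRT rule is independent of the table. The return is optional after Grade 4 neutropenia and low platelets, and unspecified for nonhematologic toxicity. The tabulated step on CRRT in the 15 mg arm lowers the daily dose.

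**Conclusion.** The point holds as a conflict between stated dosing instructions, which is more than missing detail. Five of eight combinations of arm, inhibitor and CRRT yield an empty, null or contradictory instruction. The firmest case is the 15 mg arm with a potent inhibitor after Grade 3 neutropenia: 30 mg/day under Section 7.6.2.1 against 10 mg/day under Section 7.2.1.2.

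This rests on reading the initial dose level as Table 6 labels it, and on inhibitor and CRRT adjustments applying together. The ratios are of daily milligrams; no pharmacokinetic factor is assumed.

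It would be tempting to infer that participants were misdosed or that the mortality comparison is compromised. The documents do not show that. They give no frequency for toxicity attributed to study drug coinciding with an inhibitor or CRRT, initial treatment is 14 days, and the primary analysis is ITT by assigned arm. SAP Section 3.3 reports enrollment halted at 211 participants, which limits what a text change can still achieve. It is a worthwhile, safety-relevant correction, but not one on which the trial's primary conclusion depends.

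**What to change.** Reconcile Sections 5.6, 7.2.1.1, 7.2.1.2, 7.2.1.3, 7.6.2.1, 7.6.2.2 and 7.6.2.3 with Table 6:

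- State how the inhibitor, CRRT and toxicity rules apply together.
- Define the initial dose level and a one-level reduction for a participant with an inhibitor or CRRT adjustment in force.
- Lay out the combinations of arm, inhibitor, CRRT and toxicity so that each leads to exactly one instruction.

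Which dose or rule applies in each combination is for the sponsor's clinical and pharmacology team; nothing here favors one.

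The cost is a short amendment or investigator notification, with no new data or participants. It applies before any further dosing under this protocol or reuse of the text. For participants already treated, the sponsor should identify those with an inhibitor or CRRT together with a toxicity reduction or hold, and document how they were dosed. Concomitant medications, procedures and dose modifications are already recorded on the eCRF.

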7.6.2.2. Thrombocytopenia

Transfusion support should be provided as clinically indicated.

For platelet counts $< 20 \times 10^9$ /L: hold dose until resolved to $\ge 20 \times 10^9$ /L and then resume at 1 dose level lower. If counts are stable, dose may be cautiously re-escalated to initial dose level.

Dose reductions or interruptions for nonhematologic toxicity are permitted to allow the participant to continue on study treatment. Dose adjustments for different ranges of nonhematologic toxicity are described in the following text. The objective of the dose

adjustment rules is to optimize treatment response for each individual participant while avoiding significant nonhematologic toxicities.

7.6.2.3. Other Adverse Events (Nonhematologic) Attributed to Ruxolitinib/Placebo

Recommendation for Grade 1 or 2: maintain dose level.

Recommendation for Grade 3: reduce by 1 dose level until resolved to \leq Grade 2.

Recommendation for Grade 4: discontinue from study treatment.

Medication used to treat AEs must be recorded on the appropriate eCRF.

7.7. Preparation and Dispensation

Each study site will be supplied with study drug in packaging as described in Section 7.4.

A unique medication number is printed on the study medication label.

7.7.1. Handling of Study Treatment

Study treatment must be received by a designated person at the study site, handled and stored safely and properly, and kept in a secured location to which only the investigator and designated site personnel have access. Upon receipt, all study treatment must be stored according to the instructions specified in the IB (or Pharmacy Manual). Bottles of ruxolitinib tablets should be stored at room temperature (15°C-30°C [59°F-86°F]).

Medication labels will be in the local language and comply with the legal requirements of each country. They will include storage conditions for the study treatment but no information about the participant except for the medication number.

The investigator must maintain an accurate record of the shipment and dispensing of study treatment in a drug accountability log. Monitoring of drug accountability will be performed by monitors during on-site visits or remotely and at the completion of the study (on-site or remotely). Participants will be asked to return all unused study treatment and packaging at the end of the study or at the time of discontinuation of study treatment.

The study site may destroy all unused study treatment, packaging, and drug labels locally per site policies and procedures, which are subject to review and prior approval by Incyte. If local destruction or procedure is not available, the site may return all unused study treatment, packaging, drug labels, and a copy of the completed drug accountability log to the address indicated in the Pharmacy Manual.

8. INFORMED CONSENT PROCEDURES

Eligible participants may only be included in the study after providing (witnessed, where required by law or regulation), IRB-approved informed consent (and assent, as applicable); informed consent may be obtained from a health care proxy where appropriate and/or institutionally approved method of consenting when applicable (verbal consent) as defined in their local consent form.

If applicable, in cases where the participant's representative(s) gives consent (if allowed according to local requirements), the participant must be informed about the study to the extent possible given his/her understanding. If the participant is capable of doing so, he/she must indicate agreement by personally signing and dating the written informed consent document.

Informed consent (and assent, as applicable) must be obtained before conducting any study-specific procedures (eg, all of the procedures described in the Protocol). The process of obtaining informed consent (and assent, as applicable) must be documented in the participant source documents. The date when a participant's informed consent was actually obtained will be captured in their eCRFs.

Incyte will provide to investigators in a separate document a proposed ICF that complies with the ICH GCP guidelines and regulatory requirements and is considered appropriate for this study. Any changes to the proposed consent/assent form suggested by the investigator must be agreed upon by Incyte before submission to the IRB.

Information about common side effects already known about the investigational drug can be found in the IB. This information will be included in the participant informed consent/assent and should be discussed with the participant during the study as needed. Any new information regarding the safety profile of the investigational drug that is identified between IB updates will be communicated as appropriate, for example, via an investigator notification or an aggregate safety finding. New information might require an update to the informed consent/assent and then must be discussed with the participant.

Women of childbearing potential must be informed that taking the study treatment may involve unknown risks to the fetus if pregnancy were to occur during the study and agree that in order to participate in the study, they must adhere to the contraception requirements during treatment and after discharge from hospital.

Male participants must be informed that if a female partner becomes pregnant during treatment or after discharge from the hospital and within 30 days of the last dose of study medication, contact with the female partner will be attempted to request her consent/assent to collect pregnancy outcome information.

A copy of the approved version of all consent and assent forms must be provided to Incyte after IRB approval.

9. VISIT SCHEDULE AND ASSESSMENTS

The SoA (see Table 3) lists all of the assessments and when they are performed. All data obtained from these assessments must be supported in the participant's source documentation. Any assessments outlined in Table 3 otherwise performed per standard of care may be used to satisfy study requirements.

Participants should be seen for all visits/assessments as outlined in the assessment schedule (see Table 3) or as close to the designated day/time as possible. Missed or omitted visits or assessments should not lead to automatic discontinuation. Participants who prematurely discontinue the study (see Section 10.1.1) for any reason should be scheduled for a visit (in person or remote) as soon as possible, at which time all of the assessments listed for the final visit will be performed. At this final visit, all dispensed investigational product should be reconciled, and the AE and concomitant medications should be recorded on the eCRF.

If a participant is discharged from the hospital during the study period, the clinical status evaluation with 9-point ordinal scale will be performed via telephone call (7:00 AM-12:00 PM local time) daily, except for Day 15 and Day 29 when it will be performed in clinic, when possible (telephone contact is an acceptable alternative for clinic visits). If the participant is unable to return to the clinic on Day 15 and Day 29, all scheduled assessments may be performed by telephone; local laboratory assessments may be performed on Day 15 and/or Day 29 if feasible.

